Trial Design: This study is a Phase 2b, multi-center, extension study designed to evaluate the long-term efficacy, safety, and tolerability of PRO 140 monotherapy for the maintenance of viral suppression in patients who were stable on combination antiretroviral therapy and completed 12 weeks of treatment under PRO 140_CD 01 Treatment Substitution Study without experiencing virologic failure. Consenting patients will continue to receive PRO 140 monotherapy until IP receives marketing approval or IND is withdrawn by Sponsor. There is one week overlap of existing retroviral regimen and PRO 140 at the end of the treatment extension phase in subjects who do not experience virologic failure. PRO 140 will be administered as a 350 mg subcutaneous injection weekly during treatment extension phase. Study participants will be monitored for viral rebound on a weekly basis following initiation of PRO 140 monotherapy and will re-initiate their previous antiretroviral regimen if plasma HIV-1 RNA levels rise above 400 copies/ml on two consecutive blood draws at least 3 days apart. NOTE: Patients that were enrolled under a previous Protocol version and are still receiving the 350 mg dose, have the option of increasing their dose to 700mg for the remainder of the Treatment Extension Phase. The study will have three phases: Screening Phase, Treatment Extension Phase and Follow-up Phase. Screening Phase (14 ± 3 days): This phase is designed to determine whether subjects participating in PRO 140_CD 01 Treatment Substitution study are eligible to continue PRO 140 monotherapy in the Treatment Substitution Extension study. This phase consists of a series of screening assessments designed to determine eligibility. A written informed consent from the subject will be obtained by the Investigator or suitably qualified individual before the performance of any protocol-specific procedure. This phase consists of two screening visits (SV1 and SV2) which correspond to Treatment Visits 12 and 13 of the PRO 140_CD 01 Treatment Substitution Study, respectively. Subjects participating in PRO 140_CD 01 Treatment Substitution study that have not experienced virologic failure will be approached for study participation at Treatment Visit 12 (T12). A signed informed consent form will be obtained at the T12 visit which serves as Screening Visit 1 (SV1) for the PRO 140_Treatment Substitution Extension study.	

Name of Sponsor: CytoDyn Inc.	

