1.5.2.7 PRO 140_CD 01 Study

PRO 140_CD01 study (open-label, 43 subjects, multi-center) (12-cohort 1, 28-cohort 2, 3-cohort 3) evaluated the efficacy, safety, and tolerability of PRO 140 monotherapy (350 mg subcutaneous injection weekly for up to 12 weeks) for the maintenance of viral suppression following

substitution of antiretroviral therapy in HIV-1 infected patients (with exclusive CCR5-tropic virus). Participants in this study were experienced HIV-infected individuals who were virologically suppressed on combination antiretroviral therapy. Consenting patients were shifted from combination antiretroviral regimen to PRO 140 monotherapy for 12 weeks.

Forty (43) subjects (M/F: 40/3) with median age of 55 years (26-72) and median CD4 T-cell count of 604.5 cells/mm³ (365-1240) were enrolled in the CD01 study. Overall, twenty-three out of 43 (54%) enrolled subjects completed 12 weeks of PRO140 monotherapy without experiencing virologic failure. Virologic failure was defined as two consecutive HIV-1 RNA levels of \geq 400 copies/mL separated by at least 3 days.

Of the first 40 enrolled subjects enrolled under cohort 1 and cohort 2, three subjects were found to have Dual/Mixed (D/M) tropism [1 at baseline and 2 at the time of virologic failure] and 37 subjects were found to have exclusive CCR5-tropic virus. A letter of amendment was filed to increase the planned number of subjects from 40 to 43 subjects to compensate for the 3 Dual/Mixed subjects enrolled in the study.

All virologic failure subjects who had available lab data in both studies achieved viral suppression to $<$ 400 HIV-1 RNA copies/mL, as well as viral suppression to 'Non Detectable' or $<$ 50 HIV-1 RNA copies/mL after re-initiation of ART.

The by-subject analysis of PhenoSense® Entry Assay data for PRO140, maraviroc, and AMD3100 shows no significant changes in the post-treatment IC50 and IC90 values were noted when compared with baseline values in virologic failure and non-virologic failure groups of subjects.

Anti-PRO140 antibodies were not identified in any post-treatment sample and data derived from the CD01 study further supports the favorable PRO140 PK profile data generated from both pre-clinical as well as prior Phase 1/2 clinical trials.

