3.3 ELIGIBILITY CRITERIA

3.3.1 Inclusion Criteria

Subjects must meet all of the following criteria to be included in the study:

[figure not shown]
1. Subjects who have completed 12 weeks of treatment in PRO 140_CD 01 study without experiencing virologic failure.
2. Both male and female patients and their partners of childbearing potential must agree to use appropriate birth control methods (birth control pills, barriers, or abstinence) throughout the study duration (excluding women who are not of childbearing potential and men who have been sterilized). Females of childbearing potential must have a negative urine pregnancy test prior to receiving the first dose of study drug.
3. Willing and able to participate in all aspects of the study, including use of SC medication, completion of subjective evaluations, attendance at scheduled clinic visits, and compliance with all protocol requirements as evidenced by providing written informed consent.

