8.2 DESCRIPTION OF STUDY ENDPOINTS

8.2.1 Primary Efficacy Endpoints

The primary efficacy endpoint for this study is time to virologic failure after initiating PRO 140 monotherapy.

Virologic failure is defined as two consecutive HIV-1 RNA levels of ≥ 400 copies/ml separated by at least 3 days.

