8.7.4 Efficacy Analysis

8.7.4.1 Primary Analysis

The primary analysis will be conducted on the PP population.

The primary efficacy endpoint for this study is time to virologic failure after initiating PRO 140 monotherapy.

Virologic failure is defined as two consecutive HIV-1 RNA levels of ≥ 400 copies/ml separated by at least 3 days.

The time to virologic failure for the subjects treated with PRO 140 monotherapy will be compared to a historical data (i.e., time to HIV-1 RNA viral load > 500 copies/mL of 29 days). The statistical comparison will be conducted using Wilcoxon rank sum test and the median time to virologic failure for this study will be compared to 30 days.

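### The primary test against 30 days cannot fail as written, because only patients with about 12 failure-free weeks on PRO 140 already behind them can enter

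*Protocol*

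**What the plan says.** Section 8.2.1 defines the endpoint: "The primary efficacy endpoint for this study is time to virologic failure after initiating PRO 140 monotherapy". Section 8.7.4.1 compares it with a historical "time to HIV-1 RNA viral load > 500 copies/mL of 29 days", names a Wilcoxon rank sum test, and adds that "the median time to virologic failure for this study will be compared to 30 days".

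The start of monotherapy lies in the parent study. Section 1.5.2.7 says of CD 01: "Consenting patients were shifted from combination antiretroviral regimen to PRO 140 monotherapy for 12 weeks". The Synopsis (Trial Design) describes the extension as a continuation: "Consenting patients will continue to receive PRO 140 monotherapy until IP receives marketing approval or IND is withdrawn by Sponsor".

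Entry is restricted by inclusion criterion 1 in section 3.3.1: "Subjects who have completed 12 weeks of treatment in PRO 140_CD 01 study without experiencing virologic failure". Section 1.5.2.7 reports how many could qualify: "twenty-three out of 43 (54%) enrolled subjects completed 12 weeks of PRO140 monotherapy without experiencing virologic failure". Virologic failure has the same definition in both studies: two consecutive values of at least 400 copies/mL, at least 3 days apart.

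This is the only efficacy test stated. Section 8.7.4.2 summarises the secondary endpoints descriptively, and section 8.7.4.3 repeats the primary method in the ITT population.

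**The concern.** A patient who failed in the first 12 weeks of monotherapy cannot be in this trial. If the clock starts at the beginning of monotherapy, each enrolled patient brings about 84 days in which failure was impossible by the entry rule. This is immortal time, and it is nearly three times as long as the benchmark. The null hypothesis is false before the first extension dose.

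The stated objective (section 2) is long-term maintenance of suppression in 12-week completers. A test whose result is known in advance says nothing about that objective, yet it would be reported as the trial's primary efficacy finding. As a description of PRO 140 against treatment interruption, the accompanying median would also be inflated, both by the 12 guaranteed weeks and by the absence of the 20 CD 01 subjects who did not complete 12 weeks without failure.

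**Working it through.** The protocol states no sample size, power or alpha, so there is no design figure to reproduce. Two-sided 0.05 is assumed below. A one-sample sign test is used because a rank sum test needs a second sample and the protocol supplies only a single value. A signed-rank test gives the same exact p when every value lies above 30 days.

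**Inputs**
- Benchmark: 29 or 30 days (section 8.7.4.1).
- Failure-free time at entry: 12 weeks = 84 days (section 3.3.1). TE1 falls 14 days after CD 01 visit T12 (Synopsis), and Table 1-1 gives CD 01 as 14 weeks of treatment with 12 of monotherapy.
- Qualifying CD 01 subjects: 23 of 43; 43 − 23 = 20 did not qualify (section 1.5.2.7).
- Historical curve: about half rebounded after 4 weeks and almost all by 10 weeks, i.e. 70 days (section 1.3).

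**1. Clock from the start of monotherapy, as written**
- Smallest possible failure time is about 84 days, and 84/30 = 2.8. It also exceeds the 70 days by which nearly all historical subjects had rebounded.
- P(time > 30 days) = 1, so the sample median exceeds 30 days with certainty. Censoring does not alter this, because no entrant can fail or be censored before about day 84.
- Exact two-sided p = 2 × 0.5^n:

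| n | p |
|---|---|
| 5 | 0.0625 |
| 6 | 0.031 |
| 10 | 0.002 |
| 23 | 2.4e-7 |
| 28 (planned maximum) | 7.5e-9 |

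- The rejection probability is therefore 1 for any n of 6 or more.
- Suppose the drug loses all effect at TE1 and every patient fails between days 84 and 112. Each value minus 30 lies between 54 and 82, all positive, so the p-values are unchanged.

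**2. CD 01 had already answered the 30-day question**
- 23/43 = 53.5% were failure-free at 84 days. Even if the other 20 are all counted as day-1 failures, the CD 01 median exceeds 30 days.

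**3. Effect of selection on the reported median**
- All 43 subjects: 43/2 = 21.5, so the median is reached at the 22nd failure. With 20 already counted, that is the 2nd extension failure.
- Extension subjects only: 23/2 = 11.5, so the 12th failure.
- This assumes that all 20 non-qualifiers failed, that all 23 qualifiers enrolled, and that nobody is censored earlier.

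**4. Clock restarted at TE1**
- Constant hazard at the CD 01 rate: λ = −ln(23/43)/84 = 0.00745 per day; median = ln 2/λ = 93 days; P(T > 30) = exp(−30λ) = 0.80.
- P(sample median > 30 days) = 99.9% at n = 23 and 96.7% at n = 10. P(significant sign test) = 84% (needs 17 of 23) and 38% (needs 9 of 10).
- Now let the unselected population median be exactly 30 days, with gamma frailty of variance θ: S(t) = (1 + θct)^(−1/θ), c = (2^θ − 1)/(30θ). For θ = 1, S(84) = 1/3.8 = 0.263 and S(114) = 1/4.8 = 0.208, so P(30 further days | 84) = 0.79.

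| θ | P(> 30 further days, given 84) | Rejection rate, n = 23 |
|---|---|---|
| 0 | 0.50 | 1.7% |
| 0.5 | 0.70 | 46% |
| 1 | 0.79 | 81% |
| 2 | 0.87 | 98% |

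The frailty variances are assumptions chosen to show the range.

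**The case against.** The strongest reply is that the clock may be meant to start at TE1. Section 4.2 calls TE1 the date of first treatment, the Synopsis ties the ITT population to a dose in the extension, and the wording about initiating monotherapy may be carried over from the parent protocol. HIV-1 RNA is drawn at TE2 (section 7.10.6), so on that reading failure before day 30 is possible and the test can be lost. This stands as far as it goes: the certainty belongs to the endpoint as worded. But the section 4.2 phrase sets visit timing, not the endpoint, and no section states another origin, a landmark or left truncation. Step 4 shows that a TE1 clock leaves the selection in place; only without heterogeneity between patients does the error rate stay nominal.

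Other points narrow the claim without overturning it:
- The historical subjects were not unselected in general. Section 1.3 requires at least 24 months of suppression, CD4 above 500 and RNA below 50. They were unselected only with respect to response after stopping therapy.
- The p-values come from a sign or signed-rank test, not the named rank sum test, and are illustrative. With patient-level historical data the rank sum would point the same way, since almost all historical times end by day 70 and every trial time starts near day 84.
- The n = 28 row cannot arise if only 23 qualified.
- The objective is openly conditional on 12-week completers, so a median in responders is a legitimate target. That argues for estimating it as such, not for testing it against 30 days.
- Section 8 leaves methods detail to the SAP, and the study is called proof of concept. But the protocol itself fixes the endpoint, entry rule and benchmark, and proof-of-concept status does not excuse a primary test with a known result.

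**Conclusion.** The concern holds and must be fixed. On the endpoint as written, the primary comparison is settled by inclusion criterion 1: every failure time is at least about 84 days against a benchmark of 29 or 30, and rejection is certain for any n of 6 or more. That conclusion needs only the protocol's own time origin and entry rule, plus the assumed two-sided 0.05 level for the minimum n. It does not depend on how the 20 other CD 01 subjects are classified.

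If the clock is read as starting at TE1, a win is likely but not guaranteed: 84% at n = 23 under a constant hazard at the CD 01 rate. The comparison remains biased by selection on response. On either reading a significant result would not show long-term efficacy.

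**What to change.** 1. Remove the test against 29/30 days as the primary inference, in the Synopsis and in section 8.7.4.1.
2. State the time origin in section 8.2.1. Define the primary analysis as durability in 12-week responders: Kaplan-Meier from TE1, or from the start of monotherapy with delayed entry at TE1 so that the first 12 weeks add no time at risk. Report the median and the failure-free proportions at fixed weeks with 95% confidence intervals, labelled as conditional on 12 weeks of success in CD 01.
3. If a historical comparison is still wanted, make it on all 43 CD 01 subjects from their first day of monotherapy, including the 20 who did not complete 12 weeks without failure. Say in advance how the three subjects with dual/mixed tropism and any non-virologic withdrawals are handled.

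The cost is protocol and SAP wording plus CD 01 data the sponsor already holds; no visit, dose or clinical rule changes. The sponsor gives up a guaranteed small p-value and, in any full-cohort comparison, reports a less favourable median.

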8.7.4.2 Secondary Analysis

- Proportion of participants with virologic failure after initiating PRO 140 monotherapy.
- Mean change in viral load (HIV-1 RNA levels)
- Mean change in CD4 cell count
- Change in quality of life metrics (up to TE107)

All data from the secondary endpoints will be summarized according to the variable type for the PP population:

- Continuous data summaries will include number of observations, mean, standard deviation, median, and minimum and maximum values
- Categorical data summaries will include frequency counts and percentages

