Name of Study Product: PRO 140 (Humanized monoclonal antibody to CCR5) Comparator: Historical Control	
Protocol Number: PRO 140_CD 01-Extension	Indication: Human Immunodeficiency Virus Type-1 (HIV-1) Infection

 During the Treatment Extension Phase, if virologic failure occurs or have met any other criteria for discontinuation of study treatment as specified in section 5.2 of the PRO 140_Treatment Substitution Extension Study protocol. 
Subjects who experience virologic failure (defined as two consecutive HIV-1 RNA levels of ≥ 400 copies/ml separated by at least 3 days) at any time during the Treatment Extension Phase will undergo the Virologic Failure (VF) Visit assessments and then exit the Treatment Extension Phase to enter the Follow-up Phase of the study.
 
Subjects who do not experience virologic failure will enter the Follow-up Phase of the study at the end of Treatment Extension Phase.
	

Follow-up Phase:
 
Duration of Follow-up Phase is determined based on whether or not subject has experienced virologic failure during the Treatment Extension Phase.
 
 Subjects who experience virologic failure will be followed up every 4 weeks until the viral suppression is achieved (i.e., plasma HIV-1 RNA levels return to <50 copies/mL) Subjects who do not experience virologic failure at the end of Treatment Extension Phase, will be followed up every 2 weeks for total of 4 weeks. 
➤ Note: Virologic failure subjects will have a long term safety follow up visit once a year within 2 years of completing the last VF-FU visit.
	

Duration of Study:
 
 Screening Phase: 14 ± 3 days Treatment Extension Phase: Weekly \pm allowed windows (± 3 days). Follow-up Phase: 
 Virologic Failure: Until viral suppression is achieved Non-Virologic Failure (NVF): 4 weeks 
Total Study Duration:
 
Weekly until IP receives marketing approval or IND is withdrawn by Sponsor. [Does not include additional follow-up time for virologic failure subjects]
	

Inclusion Criteria: Potential subjects are required to meet all of the following criteria for enrollment into the study.
 
 Subjects who have completed 12 weeks of treatment in PRO 140_CD 01 study without experiencing virologic failure. 	

Name of Sponsor: CytoDyn Inc.	

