8.2.2 Secondary Efficacy Endpoints

- Proportion of participants with virologic failure after initiating PRO 140 monotherapy.
- Mean change in viral load (HIV-1 RNA levels)
- Mean change in CD4 cell count
- Change in quality of life metrics (up to TE107)

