8.6.1.2 Per Protocol Population

The Per Protocol (PP) population is defined as the set of subjects who meet the ITT population requirements, and were not associated with a major protocol violation. This population will be identified before the database lock. The PP population will be the primary analysis population for the analysis of primary and secondary endpoints.

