8.6.4 Handling of Missing Data

For the per protocol analysis of efficacy endpoints there will be no imputation of missing data. However, missing data will be imputed using different methods that will be detailed in the SAP for the ITT analysis of the primary and secondary endpoints.

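### The secondary proportion with virologic failure is a count and percentage with no time point over open-ended follow-up; on the plain per-protocol reading it understates cumulative risk if leavers would later have failed

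*Protocol*

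**What the plan says.** Section 8.2.2 lists the endpoint as "Proportion of participants with virologic failure after initiating PRO 140 monotherapy", with no week. Section 8.7.4.2 repeats it and sets the method: "All data from the secondary endpoints will be summarized according to the variable type for the PP population". For a categorical variable this means: "Categorical data summaries will include frequency counts and percentages".

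Four other statements determine what that percentage will measure:

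- **Length of follow-up.** The synopsis gives the total duration as "Weekly until IP receives marketing approval or IND is withdrawn by Sponsor". A 161-week treatment phase still appears in Section 4.2 and in some footnotes to the schedule tables.
- **Exit without failure.** Sections 5.2 and 5.2.1 let subjects withdraw or stop study treatment for several reasons other than virologic failure, including a wish to go back to antiretroviral therapy (ART).
- **Denominator.** Under Section 8.6.1.2 the PP population is those who "meet the ITT population requirements, and were not associated with a major protocol violation". The ITT requirements are one dose and one post-treatment viral load, so stopping early does not in itself remove a subject.
- **Missing data.** Section 8.6.4 states: "For the per protocol analysis of efficacy endpoints there will be no imputation of missing data". For ITT the same section says that "missing data will be imputed using different methods that will be detailed in the SAP for the ITT analysis of the primary and secondary endpoints".

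**The concern.** A proportion with an event is interpretable when everyone has been observed for the same time, or when the estimate allows for those who have not. Neither holds here. A PP subject who leaves failure-free at week 10 and one who stays suppressed for three years contribute identically: one each to the denominator, nothing to the numerator. The reader cannot tell by which week the stated percentage had failed, and so cannot set it beside a figure from another study.

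If some of those who left would have failed later, the percentage also lies below the cumulative failure risk. The study's stated objective is long-term maintenance of suppression, so this percentage is likely to be read as a long-term risk, which it does not estimate.

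**Working it through.** The protocol states no target proportion, failure rate or exit rate for the extension, so there is no figure to reproduce. The check shows how far the percentage as specified can lie from the cumulative risk.

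**Inputs.** The horizon is 161 weeks, the only numeric treatment length still in the text, used purely for illustration. Assumed, not from the documents: true failure risk F by week 161 of 30%, 40% or 50%; probability E of leaving by week 161, in the absence of failure, of 0% to 50%; constant and independent hazards.

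**Formula.** With a = −ln(1 − F) and b = −ln(1 − E), the expected percentage with all PP subjects in the denominator is

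crude = a/(a + b) × [1 − (1 − F)(1 − E)].

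For F = 40% and E = 30%: a = 0.511, b = 0.357, a/(a + b) = 0.589, and 1 − 0.6 × 0.7 = 0.58. So crude = 0.589 × 0.58 = 34.2%.

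| True risk F | E = 0% | E = 20% | E = 30% | E = 50% |
|---|---|---|---|---|
| 30% | 30.0% | 27.1% | 25.5% | 22.1% |
| 40% | 40.0% | 36.2% | 34.2% | 29.7% |
| 50% | 50.0% | 45.4% | 42.9% | 37.5% |

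For exits of 20% to 50%, the shortfall runs from 30.0 − 27.1 = 2.9 points to 50.0 − 37.5 = 12.5 points. With no exits it is zero.

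**Does Kaplan-Meier recover the risk?** In simulation (4,000 runs each at N = 23, the number who completed the parent study without failure, and N = 28, the planned maximum), with annual dropout of 0%, 5%, 10% or 20%, the mean Kaplan-Meier estimate at week 161 was 29.8% to 30.1% for a true 30% and 49.8% to 50.2% for a true 50%. At 5%, 10% and 20% annual dropout the crude percentage was 27.9%, 25.8% and 22.1% for a true 30%, and 46.7%, 43.5% and 37.5% for a true 50%.

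**Effect of the missing horizon alone.** Take no exits and a hazard giving 50% at week 161. The percentage by week w is 1 − 0.5^(w/161): 20% at week 52, 37% at week 107 and 67% at week 260. The risk per unit time is the same throughout; only the length of follow-up differs, and the protocol ties that length to approval or withdrawal of the IND.

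**Effect of the denominator rule.** Suppose 28 subjects, 8 failures and 6 non-failure exits. All subjects in the denominator: 8/28 = 28.6%. Leavers excluded: 8/22 = 36.4%. Leavers counted as failures: 14/28 = 50.0%.

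**The case against.** The strongest reply is that this is a descriptive secondary endpoint in a proof-of-concept study of up to 28 subjects. No test or decision rests on it. The primary endpoint, time to virologic failure, carries the durability objective and uses when each subject failed. Detailed methods go to the SAP, and listing counts and percentages does not forbid adding time points or intervals. The observed share who failed on treatment is also a legitimate quantity, and Kaplan-Meier is itself biased if exits track rising viral load.

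Much of this stands. It limits the severity, it means the absence of a planned confidence interval is not a fault in its own right, and it is why the count should stay. It does not remove the point: Section 8.7.4.2 itself fixes the PP summary, and Section 8.6.4 rules out imputation for it.

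A reader might infer more than the documents support:

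- *That leavers are declared non-failures.* The protocol never says so. It follows from the plain PP denominator only. The ITT analysis of the same endpoint will impute by methods left to the SAP.
- *That understatement is certain.* It requires exits, among them subjects who would later have failed, and the full denominator. If leavers were dropped instead, the direction reverses: 31.8% to 38.7% for a true 30%, and 52.2% to 60.0% for a true 50%, at 5% to 20% annual dropout.
- *That the figure will drift across successive data cuts.* No efficacy interim is planned, and the safety look in Section 8.5 comes after subjects complete or stop treatment. The horizon is undefined because the end of treatment is undefined.
- *That this is the main durability result.* It is secondary. How the primary analysis treats censoring is a separate matter and is not relied on here.

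**Conclusion.** The point holds for the PP summary in Section 8.7.4.2. As written, the percentage has no horizon and pools unequal follow-up. On the plain denominator it understates cumulative risk if subjects who exit would later have failed. The size, about 3 to 12.5 points, rests wholly on assumed 161-week risks of 30% to 50%, assumed exits of 20% to 50%, and constant, independent hazards. It is zero without exits. The missing time point is a weakness whatever the exit rate. Severity: should-fix.

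**What to change.** In Section 8.7.4.2, report Kaplan-Meier cumulative virologic failure at fixed extension weeks, for example 24, 48, 96 and 144 counted from TE1, with 95% confidence intervals and numbers at risk. Censor at the last HIV-1 RNA taken on PRO 140 monotherapy. Keep the observed count and percentage beside it, with the denominator stated. Because exits may be informative, add one sensitivity analysis that counts non-failure exits from monotherapy as failures.

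The cost is a few lines of text and minor programming. The viral loads are already scheduled under Section 7.10.6, so no new data are needed. The reported failure figure may be less favourable.
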